#### PROTOCOL SUMMARY:

Long title: Antibody-level Based Analysis of COVID Convalescent Serum

Short title: ABACCuS

Protocol Date: August 13, 2020

Clinical Phase: Phase 2

**Blinding and Randomization**: Double-Blinded to Antibody Content of Convalescent

Plasma, Not Formally Randomized

IND Sponsor: Beaumont Health

**Conducted by**: Beaumont Health Beaumont Hospital, Royal Oak

Beaumont Hospital, Troy

Beaumont Hospital, Grosse Pointe

Beaumont Hospital, Dearborn

Beaumont Hospital, Taylor

Beaumont Hospital, Trenton

Beaumont Hospital, Wayne

Beaumont Hospital, Farmington Hills

Trial Oversight

[name] PhD, Principal Investigator

[name], Sub-Investigator

[name], Sub-Investigator

[name], Sub-Investigator

[name] MHSA, Sub-Investigator

[name], Sub-Investigator

[name], Sub-Investigator

[name], Biostatistician

[name], MS, Research Director

Beaumont Hospital, Royal Oak – [name], Sub-Investigator

Beaumont Hospital, Troy – [name], Sub-Investigator

Beaumont Hospital, Grosse Pointe – [name], Sub-Investigator

Beaumont Hospital, Dearborn – [name], Sub-Investigator

Beaumont Hospital, Taylor – [name], Sub-Investigator

Beaumont Hospital, Trenton – [name], Sub-Investigator

Beaumont Hospital, Wayne – [name], Sub-Investigator

Beaumont Hospital, Farmington Hills – [name], DO, Sub-Investigator

# **LIST OF ABBREVIATIONS**

ADR: Adverse Drug Reaction

ADE: Antibody Dependent Enhancement of infection

AE: Adverse Event/Adverse Experience

CDC: United States Centers for Disease Control and Prevention

CFR: Code of Federal Regulations

CLIA: Clinical Laboratory Improvement Amendment of 1988

COI: Conflict of Interest

COVID-19: Coronavirus Disease

CRF: Case Report Form

DSMB: Data and Safety Monitoring Board

EMR: Electronic Medical Record EUA: Emergency Use Authorization FDA: Food and Drug Administration

GCP: Good Clinical Practice

HBV: Hepatitis B virus HCV: Hepatitis C virus

HIV: Human immunodeficiency virus HTLV: Human T-cell lymphotropic virus

IB: Investigator's Brochure

ICF: Informed Consent (Informed Consent Form) ICH: International Conference on Harmonization

ICU: Intensive Care Unit

IND: Investigational New Drug Application

IRB: Institutional review board

ISBT: International Society of Blood Transfusion MERS: Middle East Respiratory Syndrome

NP: Nasopharyngeal PI: Principal Investigator

PPE: Personal Protective Equipment

RT-PCR: Reverse Transcriptase Real-Time Polymerase chain reaction

SAE: Serious adverse event

SARS: Severe Acute Respiratory Syndrome

SARS-CoV-2: Severe Acute Respiratory Syndrome Coronavirus 2

TACO: Transfusion-associated circulatory overload

TRALI: Transfusion-related acute lung injury

**UP: Unanticipated Problem** 

**Sample Size:** 500 (300 serious but non-intubated patients, 200 intubated patients)

# **Study Population:**

Group A: Hospitalized COVID-19 patients ages ≥18 years with respiratory symptoms, requiring >6L of oxygen to maintain O2 saturation >92%. Patient may not require intubation, and may be admitted for no longer than 14 days.

Group B: Hospitalized COVID-19 patients ages ≥18 years requiring intubation.

Study Duration: May 15, 2020 to December 31, 2022

Study Design: This phase 2 trial will evaluate the efficacy and safety of SARS-CoV-2 convalescent plasma as treatment for confirmed COVID-19 respiratory disease (as defined in the inclusion criteria). Adults 18 years of age and older may participate. Patients may be enrolled in group A within 14 days of admission to the hospital and may be enrolled in group B at any time after intubation. A total of 300 eligible subjects with significant oxygen requirements and 200 eligible subjects who require intubation will be included in the study. They will receive convalescent plasma from either a patient who has recovered from COVID-19 or from an asymptomatic carrier with confirmed IgG against SARS-CoV-2. Subjects will not be randomized but the amount of anti-SARS-CoV-2 IgG and IgA in any unit of plasma will not be known when the unit is assigned to the patient. This will allow us to examine the relationship between the amount of anti-SARS-CoV-2 antibody and outcomes. Analysis will be based on measurement of optical density of the IgG level in the unit of plasma the patient is randomly supplied by the blood bank. While investigators and patients will be aware the patient is receiving a unit of COVID-19 convalescent plasma, both the investigators and the patients will be blinded to the antibody content of that unit.

Assessment in all subjects: Given the issues with the pandemic such as limitations on PPE, and the need for strict isolation, patient data will be limited to that which is acquired from the EPIC EMR (in use at our institution) but not from face to face interview with the patient. The data will be supplemented as possible with phone interview with the patient or their LAR. Consenting will be e-consent based using RedCap with the consent form e-mailed to the patient or the LAR for review prior to the actual consent process. Consent will be obtained over the phone and with a witness: the consent provider and the witness will both document the consent process within the patient's chart in the EPIC EMR.

**Study Product:** COVID-19 convalescent plasma (1 unit; ~300 mL) The product will be produced by Verseti Blood Bank (or other acceptable, blood bank licensed to produce plasma) using standard screening and safety procedures. The product may be procured from patients who have: 1) been symptom free for 14 days and screen negative via NP swab or 2) symptom free for at least 28 days or 3) individuals who have never had symptoms of COVID-19 but were found to have elevated anti-SARS-CoV-2 IgG by a serology test deemed to be of acceptable quality and fitting the current guidance by the FDA. Current protocols from Verseti do not screen for antibody level in COVID convalescent plasma, but Verseti retains a residual sample for later testing. Any emerging FDA guidance will be followed. From each unit, immediately after thawing, 2 mL will be removed, 1 mL for SARS-CoV-2 IgA and IgG tests and 1 mL to be held at -80°C for future neutralizing antibody testing.

# 1. Background

# 1.1 COVID-19: A Major Pandemic Currently Affecting the Entire World

In late 2019 the first cases of what has come to be named COVID-19 were noted in Wuhan China. COVID-19 is caused by a novel coronavirus now designated SARS coronavirus-2 (SARS-CoV-2). As of 5/3/2020, the total number of diagnosed cases of COVID-19 worldwide is 3,566,487 with 248,302 deaths and 1,154,550 have been documented to have recovered, and in the United States there are 1,188,122 cases, 68,598 deaths, and 178,263 recovered. Michigan as a state has been disproportionately impacted, at one point ranked third highest number of cases, though due to stay at home orders and other mitigation strategies it has more recently fallen to seventh. It remains third highest for deaths due to COVID-19, and it has the highest percentage of cases leading to mortality in the US. As of 5/3/1010 in Michigan there are currently 43,754 cases, 4,049 deaths, and recovered is not currently available. The first death in Michigan was reported from Beaumont, Wayne. Eighty percent of the cases in Michigan fall within the tri-county Detroit metropolitan area which Beaumont Health serves.

The most common presenting symptoms of COVID-19 are fever, cough, and shortness of breath⁴ and the disease presentation ranges from asymptomatic to mild to an overwhelming inflammatory response leading to acute respiratory distress syndrome (ARDS) and cytokine release syndrome and ultimately death. The actual mortality of the disease is currently unknown but estimates from China suggest a mortality rate of 3.6% (95% CI 3.5–3.7)⁵. In the United States mortality estimates to date indicate that fatality was highest in persons aged ≥85, ranging from 10% to 27%, followed by 3% to 11% among persons aged 65–84 years, 1% to 3% among persons aged 55-64 years, <1% among persons aged 20–54 years, and no fatalities among persons aged ≤19 years⁶. The overall mortality rate ~1.5% which varies day to day (0.8%-2.6% depending on the day it is calculated)⁶. Importantly current mortality numbers for the United States are based on a time when the health care system was not overwhelmed. When analyzing the mortality of COVID-19 in Italy, a country whose health care system can no longer handle the patient load caused by this disease, the mortality is currently estimated at 9.3%².

Those at high risk for progression to severe illness include people over the age of 65, people who live in a long term care facility, people with chronic lung disease, people with heart disease, immunocompromised patients, people who are obese (BMI≥40), and people with other chronic medical conditions such as diabetes, renal failure, and liver disease. At Beaumont Health we have noted a trend that severe cases tend to be male, African American, with diabetes and hypertension (unpublished data).

#### 1.2 Current Treatment of COVID-19

There is currently a single treatment approved by the FDA under emergency use authorization, remdesivir. Remdesivir is an experimental medication developed for the treatment of Ebola virus and active against RNA viruses including COVID. Remdesivir was studied in an NIH sponsored clinical trial in COVID-19 and did not show a statistically significant reduction in mortality, but did show a decrease in length of the disease by 31%. At this time availability of remdesivir remains low and exactly where it best fits in the therapy of COVID-19 remains unclear.

There have been numerous other approaches to therapy tried including hydroxychloroquine and azithromycin based in part on the study of Gautret et al which revealed promising outcomes that were unable to be duplicated by Molina et al. Other studies of hydroxychloroquine in more severely ill COVID-19 patients failed to show a significant benefit  though it remains to be seen if it is useful early in the course of the disease to prevent progression or as prophylaxis. Lopinavir-ritonavir is a repurposed HIV protease inhibitor which showed good activity against SARS but has failed to show activity against COVID-19. There are numerous other compounds in research studies, but none have yet shown any benefit.

# 1.3 Convalescent Plasma as a Therapy for Infectious Diseases

It is not clear how long convalescent plasma therapy has been used to treat infectious diseases but the first protocolized use was in the 1890s as a means to treat Diphtheria. The use continued in the 20th century as a means to treat Scarlet Fever and Pertussis and was the only means of treating certain infectious diseases prior to the widespread availability of antimicrobial therapy in the 1940s. The use of convalescent plasma to treat viral diseases, including severe respiratory diseases is widespread but unfortunately the studies are generally poorly controlled for bias. Notably convalescent plasma therapy was used to treat influenza during the Spanish Flu Pandemic of 1918-1920 with a suggestion of success multiple studies, a meta-analysis of the use of convalescent plasma for the Spanish Flu was published in 2006. More recently convalescent plasma was used as a potential treatment in the 2013 African Ebola epidemic. A small non-randomized study in Sierra Leone revealed a significant increase in survival for those treated with convalescent whole blood relative to those who received standard treatment while other studies were not as positive.

# 1.4 Convalescent Plasma as a Therapy for Coronaviruses

SARS-CoV-2 is the most recent coronavirus to impact humans, while there are literally hundreds, perhaps even thousands of coronaviruses only 7 have been shown to affect humans. There are 4 coronaviruses which are causes of the common cold; 229E, NL63, OC43, and HKU1. There are 2 other coronaviruses that have been associated with epidemics and high mortality, SARS-CoV, the etiologic agent of SARS, and MERS-CoV, the etiologic agent of MERS. For both of these epidemics the high mortality and lack of effective treatments led to use of convalescent plasma in an attempt to save lives.

A number of case series of patients treated with convalescent plasma for SARS have been published and were reviewed in a meta-analysis in 2015 by Mair-Jenkins et al. Three of the reports included a single patient each, one report was a series of 3 health care workers who received plasma.

The first study with a reasonable number of patients reported 19 patients who received plasma after steroids vs 21 patients who only received steroids. This study reported that no one in the plasma arm died where 5 in the steroid arm died. However the study had multiple issues, it was not randomized, the steroid group had significantly higher comorbidities, and 9 members of the steroid group crossed over and received plasma. They concluded that plasma was associated with a significant decrease in mortality (p=0.049) and that receiving plasma after day 16 was associated with a poor clinical response (based on the crossover group). The also recognized that this may simply have been due to the control group receiving steroids which was later shown to be

contra-indicated in SARS.

The largest case series was 80 patients in Hong Kong who received convalescent plasma. Of the 80 patients, 33 had a good outcome, which was defined as discharge by day 22 from onset of the disease, 47 had a poor outcome which was defined as death by day 22 from onset of the disease or continued need for hospitalization after day 22. In this study the overall mortality rate among the 80 patients was 12.5% whereas the overall mortality rate in Hong Kong was 17%. Sub-analysis of the patients who received convalescent plasma also noted that those who received convalescent plasma before 14 days did better than those who received it after 14 days.

Both studies involving a larger number of patients noted that there were no adverse events associated with receiving convalescent plasma and both studies noted that there were better outcomes when plasma was given before 14 or 16 days. The choice to limit Group A in this study to patients admitted no longer than 14 days is based on these observations.

While there were clearly attempts to use convalescent plasma for MERS, there are no published cases series and only a single case report documenting a patient treated with convalescent plasma who developed TRALI. Unlike SARS and COVID-19, MERS has a very low rate of person to person spread. An analysis of MERS antibody levels in patients with MERS or suspected MERS, healthcare workers with confirmed exposure to MERS, and household contacts of patients with MERS was performed in 2015. The study had numerous issues, including the fact that very few participants had laboratory confirmed MERS and the timing of serology testing after infection or exposure was highly variable, however it showed very few had developed significant antibody levels making the use of convalescent plasma in MERS questionable and raising the concern that simply using plasma from patients who recovered from a coronavirus infection may not have adequate antibodies for a therapeutic effect.

#### 1.5 Convalescent Plasma as a Therapy for COVID-19

To date there have been 6 case series published using COVID-19 convalescent plasma as a treatment. In addition, there was a meta-analysis performed of the initial 5 case series. The various case series treated anywhere from 2 to 6 patients and in 5 of the reports all patients survived. However, when the patient populations in these studies are looked at, even when described as severe, cases often were not actually severe at the time they received convalescent plasma all but had been severe earlier in their admission. In fact, one patient in a series was already discharged from the hospital but called back in and given a dose of convalescent plasma because they had a positive PCR for SARS-CoV-2 despite clinical improvement.

In the last case series 21 patients were eligible for plasma but only 6 received it due to the limited availability of convalescent plasma and ABO compatibility. The mortality in the treatment group was 5/6 and in the control group was 14/15. The patients who received convalescent plasma had a higher clearance of the virus (p=0.005) and a longer survival period (p=0.029) but no improvement in mortality.

It is important to note that in the various case series, with few exceptions there was no measurement of anti-SARS-CoV-2 antibody in the convalescent plasma and no specific protocol under which it was given. The patients were highly heterogeneous, the

definition of a unit of plasma by volume varied, and the volume of plasma given varied from 200 ml to 2400 ml with no clear reason behind dosing additional units other than lack of patient improvement.

#### 1.6 Mechanism of Action

Convalescent antibody therapy involves the administration of plasma from persons recovered from an infection to a susceptible or ill individual. It is assumed, the plasma contains antibodies against the infectious agent but this has frequently not been confirmed in prior studies.

It is intuitively obvious that if convalescent plasma is efficacious for the treatment of an infection that the mechanism of action would be passive antibody therapy where antibodies against the pathogen lead to neutralization of the pathogen. However, other mechanisms may be possible, such as antibody dependent cellular cytotoxicity and/or phagocytosis. It has also been suggested that there are multiple ways in which convalescent plasma can lead to antibody regulated immunomodulation which in turn leads to down regulation of the hyper-inflammatory reaction associated with COVID-19.

One study examining the convalescent plasma from SARS patients found increased levels of multiple inflammation inhibitors in the plasma that were completely unrelated to the antibodies present.

Given that many of the patients who recovered from COVID-19 in the published case series were intubated long past the time when it was likely active virus was still present to be neutralized and long past the time when they should have developed their own neutralizing antibodies, there may be an as yet undefined mechanism to the activity of convalescent plasma.

# 2. Research Design

# 2.1 Objectives

**Group A Primary Efficacy Objective:** Evaluate the association between efficacy of treatment with COVID-19 convalescent plasma and the amount of Anti-SARS-CoV-2-spike protein IgG as assayed by the EUROIMMUN Anti-SARS-CoV-2 assay.

# **Group A Primary Efficacy Endpoint:** Avoidance of intubation at 28 days. **Group A Secondary Efficacy Endpoints:**

- **1.** Final outcome on a 7-point ordinal scale
- **2.** Cardio-circulatory arrest (at any time)
- 3. Renal failure, as measured by RIFLE criteria
- 4. Liver failure, as measured by elevation of ALT and AST to 5x the upper limit of normal or significant worsening of current liver failure with rise in transaminases of >25%
- 5. Evidence of cytokine storm based on measurement of inflammatory markers
- **6.** Type and duration of respiratory support
- 7. Requirement of pressor support
- 8. ICU mortality
- **9.** ICU length of stay
- **10.** In hospital mortality
- **11.** 28-day mortality
- **12.** Length of stay
- **13.** Ventilator-free days
- **14.** Readmission rate
- **15.** Patient level of anti-SARS-CoV-2 IgG at the following times: prior to transfusion, 1-hour post-transfusion, 24 hours post-transfusion, 72 hours post-transfusion, 7 days post-transfusion, every 7 days until discharge, day of discharge.
- **16.** Evaluate the rates, levels (based on CT values) and duration of SARS-CoV-2 RNA in nasopharyngeal swabs using RT-PCR amongst the anti-SARS-CoV-2 convalescent plasma at the following times: prior to transfusion, 24 hours post-transfusion, 72 hours post-transfusion, 7 days post-transfusion, and 14 days post-transfusion.

# **Group A Investigational Efficacy Objectives:**

- 1. Evaluate the efficacy of treatment with COVID-19 convalescent plasma in relation to the amount of Anti-SARS-CoV-2-spike protein IgA as assayed by the EUROIMMUN Anti-SARS-CoV-2 assay.
- 2. Evaluate the efficacy of treatment with COVID-19 convalescent plasma in relation to the amount of both Anti-SARS-CoV-2-spike protein IgG and IgA as assayed by the EUROIMMUN Anti-SARS-CoV-2 assay.

All primary and secondary efficacy endpoints for the study will be re-evaluated based on levels of IgA for investigational objective #1 and based on combined levels of IgG and IgA for investigational objective #2

**Group B Primary Efficacy Objective:** Evaluate the association between efficacy of treatment with COVID-19 convalescent plasma in relation to the amount of Anti-SARS-CoV-2-spike protein IgG as assayed by the EUROIMMUN Anti-SARS-CoV-2 assay.

# Group B Primary Efficacy Endpoint: Mortality at 28 days.

- Group B Secondary Efficacy Endpoints:
  - **1.** Final outcome on a 7-point ordinal scale
  - **2.** Cardio-circulatory arrest (at any time)
  - 3. Renal failure, as measured by RIFLE criteria
  - 4. Liver failure, as measured by elevation of ALT and AST to 5x the upper limit of normal or significant worsening of current liver failure with rise in transaminases of >25%
  - **5.** Evidence of cytokine storm based on measurement of inflammatory markers
  - **6.** Type and duration of respiratory support
  - 7. Requirement of pressor support
  - 8. ICU mortality
  - **9.** ICU length of stay
  - **10.** In hospital mortality
  - **11.** Length of stay
  - **12.** Days from transfusion till end of ventilator support in survivors
  - **13.** Ventilator-free days
  - 14. Readmission rate
  - **15.** Patient level of anti-SARS-CoV-2 IgG at the following times: prior to transfusion, 1-hour post-transfusion, 24 hours post-transfusion, 72 hours post-transfusion, 7 days post-transfusion, every 7 days until discharge, day of discharge.
  - **16.** Evaluate the rates, levels (based on CT values) and duration of SARS-CoV-2 RNA in nasopharyngeal swabs using RT-PCR amongst the anti-SARS-CoV-2 convalescent plasma at the following times: prior to transfusion, 24 hours post-transfusion, 72 hours post-transfusion, 7 days post-transfusion, and 14 days post-transfusion.

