#### 2.2 Data collection

The following data points will be gathered for all patients in the study while inpatient. Patients discharged prior to 28 days will receive a phone call to determine their 28 day outcome and patients enrolled in the study will be monitored for 90 days from discharge to determine if there is a readmission and the reason for the readmission.

**COVID-19 Presentation:** Collected on enrollment, see form on page 30.

**Demographics**: Collected on enrollment, see form on page 31.

Medical History: Collected on enrollment, see form on page 31.

Concomitant Medications: Collected on enrollment, see form on page 31.

Vital Signs: Collected daily from enrollment to discharge, see form on pages 30 and 32. Laboratory Values: Collected daily from enrollment to discharge, patient is required to have a CBC with differential, a CMP, a ferritin and a CRP. On enrollment and weekly the patient must have an IL-6, D-Dimer, procalcitonin, LDH, fibrinogen, ESR, and CK. IL-6 and LDH, other laboratory values will be recorded when obtained through standard of care. See form on page 32.

Clinical Status: Collected daily from enrollment to discharge, see form on page 32.

**Medications:** Collected daily from enrollment to discharge, see form on page 33.

Serology Values: Collected per schedule, see form on pages 34 and 35.

PCR Values: Collected per schedule, see form on page 36

Safety Data: Collected for first 24 hours after transfusion, see form on page 37.

**Outcomes:** Collected at discharge or death, see form on pages 38 and 39.

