#### 2.4 Schedule of events

Study Period	Screening	Baseline	Treatment		Follow Up a					
Day	-1 to 0	0	0	D	1	3	7	14	21	28
Eligibility								,	,	
Inclusion/Exclusion	Х									
Informed consent	Х									
Demographics and	V									
medical history form	X									
Initial data collection	Х									
form	^									
Type and Screen	Х									
Pregnancy Test	Х									
Study Procedures										
Plasma transfusion			X							
Vital signs			Xp							
Physical exam c	X		Xd		Χ		Χ			
Daily vital signs, clinical										
and laboratory values				Χ						
form										
Daily medications form				Χ						
Adverse event		X	X	Х						
monitoring				^						
Serology collection form		X	X		Χ	Χ	Χ	Χ	Χ	Xe
Outcome form										Xf
Laboratory Testsg				_	•	,	,			•
CBC with differential		X		Χ						
CMP		Χ		Χ						
Ferritin		Χ		Χ						
Fibrinogen		Χ					Χ	Χ	Χ	Χ
CRP		Χ		Χ			Χ	Χ	Χ	Χ
ESR		Χ					Χ	Χ	Χ	Χ
Creatine Kinase		Χ					Χ	Χ	Χ	Χ
D-Dimer		Χ					Χ	Χ	Χ	Χ
LDH		Х					Χ	Χ	Χ	Χ
Interleukin-6		X					Χ	Χ	Χ	Χ
Triglycerides		Χ					Χ	Χ	Χ	Χ
Procalcitonin		Χ					Χ	Χ	Χ	Χ
Anti-SARS-CoV-2 IgA			X h		Χ	Χ	Χ	Χ	Χ	Xi
Anti-SARS-CoV-2 IgG			X h		Χ	Χ	Χ	Χ	Χ	Xi
SARS-CoV-2 RT PCR			Xj		Χ	Χ	Χ	Χ		

- a Column D are obtained daily, day 1 and 3 are obtained 24 hours (+/- 1 hour) from transfusion end, day 7, 14, 21, and 28 are obtained any time on that calendar day.
- b Standard vital signs for transfusion of blood products will be performed.
- c Given the issues with isolation and PPE, the exam of the attending physician's team or the pulmonary critical care team can be used.
- d Only if needed due to acute reaction.
- e After 28 days will be collected every 7 days +/- 1 day till discharge.
- f Outcome form to be filled out on final day of admission if prior to 28 days or at 28 days, after 28 days a second outcome form to be filled out on final day of admission, readmission will be tracked for 90 days.
- g All laboratory tests from this list which are obtained as standard of care will be tracked, baseline labs within 24 hours are acceptable and do not need to be reordered.
- h To be drawn within 1 hour prior to transfusion and 1 hour post-transfusion completion (no earlier than 1 hour but up to 75 min post transfusion).
- i After day 28 this will be drawn every 7 days +/- 1 day while participant remains hospitalized.
- j To be obtained within 1 hour prior to transfusion.

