**Secondary Outcomes:** Analyses of all secondary outcomes will use a 0.3% significance level based on the Bonferroni correction for 16 tests. Final outcome measured on a 7-point ordinal scale will be analyzed using standard linear regression,

although we will also consider proportional odds models should the range of the scale actually used be small (i.e., only 3-4 categories appear in the data). We will not use splines for the standard linear regression, but will use splines if a proportional odds model is fit to the data. We will use the same logistic regression approach as for the primary outcomes for all binary secondary outcomes (cardio-circulatory arrest, renal failure, liver failure, evidence of cytokine storm, pressor support required, and readmission).

We anticipate a small number of total number of mortality events for Group A. Should mortality for Group A be small, we will use Fisher's exact test based on categorizing the unit received by each patient as either low vs. high for amount of Anti-SARS-CoV-2-spike protein IgG. The cutoff for categorizing units will be based on either median amount or based on the cutoff determined by the Bayesian log-binomial piecewise model. For Group B, all secondary mortality outcomes will be analyzed the same as for the primary outcome. Should the number of events for any specific type of mortality (e.g., ICU mortality) prove small, we will use the approach used for analyses of Group A.

We will use a generalized linear model with splines to analyze all duration types of variables (duration of respiratory support, ICU length of stay, total length of stay). We will consider using normal, log-normal, and gamma distributions, along with appropriate links.

Type of respiratory support will be analyzed using a multinomial regression with splines for antibody amount, although we will also consider using Fisher's exact test by categorizing the unit received by each patient as either low vs. high for amount of Anti-SARS-CoV-2-spike protein IgG.

We will use either standard linear regression or Poisson regression for ventilator-free days, including splines.

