	Carron (1) No limitation	ig supplemental asive ventilation	O 2 or high flo	O (4) Req w O 2 device	luiring supp			
Cardio-circulatory an	` '	ys of transfusion	on: Y/N		If so c	late:		
Renal failure by RIFLE criteria within 28 days of trans				Y/N	If so c	date:		
	B days of transfu T or AST >5x three rsening of preex	ne upper limit c			If so o	late:		
Evidence of cytokine	storm based or	n inflammatory	markers:	Y/N	If so c	late:		
Days on ventilator: _	Days off	ventilator:	_ Days o	on coldflov	N:			
Days on CPAP:	Days on I	BIPAP:	Days o	Days on non-rebreather:				
Days on NC:	Days on I	Hiflo NC:	_ Discha	Discharge on new home O 2 : Y/N				
Requirement of pres	sor support: Y/N							
Pressors used	d and dates of u	se:						
In hospital mortality: Length of Stay: Readmission: Y/N	_ ICU Leng	days: Y/N th of Stay:	<del></del>			date:		
	55 4.49			<del> </del>	55 6			
Signature of coordinate	or			Date		-		

Date

Signature of Investigator reviewing data

ABACCuS Final Outcor	me Form Group A:		
Patient Initials/Study ID:		Date of Enrollment:	
Plasma Unit Used:		Date and Time of Transfusion:	
Primary Outcome:			
Was the patient intubated	d after the transfusion: Y/N		
If intubated: Da	ate of intubation:	Study Day #:	
Secondary Outcomes:			
O Hospitalized, O O	int ordinal scale: (1) No limitations on activities (3) Not requiring supplemental O (5) On non-invasive ventilation of (6) On invasive mechanical ventif (7) Deceased	$O(4)$ Re high flow $O_2$ devi	equiring supplemental O 2
Cardio-circulatory arrest after transfusion: Y/N		If so date:	
Renal failure by RIFLE criteria after transfusion: Y/N		If so date:	
	fusion: Y/N or AST >5x the upper limit of e ening of preexisting liver failure		If so date: AST of >25%: Y/N
Evidence of cytokine s	torm based on inflammatory m	arkers: Y/N	If so date:
Days on ventilator:	Days off ventilator:	Days on coldflo	ow:
Days on CPAP:	Days on BIPAP:	Days on non-rebreather:	
Days on NC: Days on Hiflo NC:		Discharge on new home O 2 : Y/N	
Requirement of presso	or support: Y/N		
Pressors used a	and dates of use:		
In hospital mortality: Y/Length of Stay: Readmission: Y/N		_	If so date:
Signature of coordinator		Date	
Signature of Investigator reviewing data		Date

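### The arrest endpoint has no fixed window, so the time in which an arrest can be counted depends on survival and length of stay, which the plan expects to vary with IgG in Group B

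*Combined protocol and SAP*

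**What the plan says.** - **Endpoint lists (section 2.1, item 2 of the secondary efficacy endpoints in Groups A and B):** "Cardio-circulatory arrest (at any time"). Renal failure (item 3) and liver failure (item 4) carry no window at all.
- **28 Day Outcome Form, Group A:** the arrest line is broken in the PDF text and only "ys of transfusion" survives of its window. The form's title and the next line, "Renal failure by RIFLE criteria within 28 days of trans", support reading it as 28 days from transfusion.
- **Final Outcome Form, Group A:** "Cardio-circulatory arrest after transfusion: Y/N". This has a start but no end.
- **Timing of the forms (section 2.4, footnote f):** the first form is completed at discharge or at day 28. For longer stays there is "after 28 days a second outcome form to be filled out on final day of admission".
- **Period of collection (section 2.2):** "The following data points will be gathered for all patients in the study while inpatient". For early discharges, "Patients discharged prior to 28 days will receive a phone call to determine their 28 day outcome"; arrest is not named as part of that call.
- **Analysis (section 3.1, Secondary Outcomes):** "We will use the same logistic regression approach as for the primary outcomes for all binary secondary outcomes". Arrest is the first outcome named there. The covariates carried over from the primary model are age, gender and race. Neither the source form nor the window is stated.
- **No Group B outcome form appears in the documents.** For Group B only the open wording in section 2.1 can be checked.

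**The concern.** A yes/no endpoint analysed by logistic regression is comparable between patients only if each is observed over the same period. Here the open wording, combined with inpatient-only collection, makes the period equal to the hospital stay. It is short for patients who die or go home early and can run well past day 28 for those who survive and stay.

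That would be mere noise if length of observation were unrelated to IgG. In Group B the plan expects otherwise: section 3.2 assumes 28-day survival rising from 25% to 50% with high-IgG units. If that is right, high-IgG patients have more time in which to have a recorded arrest, and a unit that keeps patients alive could appear to cause arrests.

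There is also a choice left open. A Group A patient whose first arrest falls on day 35 is a No on the 28-day form and a Yes on the final form, and section 3.1 does not say which is tested. The same applies to renal failure, which is limited to 28 days on one form and open after transfusion on the other.

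**Working it through.** The documents give no arrest rate, length of stay or figure that depends on the window, so there is no plan figure to reproduce. What follows is an illustration of direction and rough size in Group B.

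**Inputs from section 3.2:** 28-day survival of 25% (low IgG) and 50% (high IgG).

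**Assumptions not in the documents:** constant daily hazards; arrest hazard h = 0.005 to 0.02 and discharge hazard q = 0.01 to 0.04, each the same at both IgG levels (so IgG has no true effect on arrest); observation ends at first arrest, death or discharge; terminal arrests are not counted.

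**Step 1. Daily death hazard, d = -ln(survival)/28**
- Low IgG: -ln(0.25)/28 = 0.0495
- High IgG: -ln(0.50)/28 = 0.0248

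**Step 2. Open window: probability of a recorded arrest = h/(h + d + q).** Central case h = 0.01, q = 0.02:
- Low IgG: 0.01/0.0795 = 12.6%
- High IgG: 0.01/0.0548 = 18.3%
- Apparent risk ratio: 1.45, with no true effect. Mean days at risk, 1/(h + d + q), are 12.6 and 18.3.

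**Step 3. 28-day cap: multiply by 1 - exp(-28(h + d + q))**
- Low IgG: 0.126 x 0.892 = 11.2%
- High IgG: 0.183 x 0.784 = 14.3%
- Apparent risk ratio: 1.28

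**Step 4. Range over all nine combinations (h = 0.005, 0.01, 0.02; q = 0.01, 0.02, 0.04)**

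| Window | Apparent risk ratio, high v low IgG |
|---|---|
| Open, to discharge or death | 1.29 to 1.62 |
| Capped at day 28 | 1.23 to 1.30 |

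**Step 5. Chance of a false finding at the 0.3% level.** As a simplification, take two groups of 100 and compare proportions. The rejection probability is 3.1% with the open window and 1.0% with the cap in the central case (ranges 0.8% to 10.8% and 0.5% to 2.5%).

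**Step 6. Terminal arrests.** The plan does not say whether the arrest at death counts. If a fraction f of deaths is recorded as arrest, the open-window probability becomes (h + f x d)/(h + d + q). Setting the two IgG levels equal gives f = h/(h + q). In the central case that is 0.01/0.03 = one third; the range is 0.005/0.045 = 0.11 to 0.02/0.03 = 0.67. Above that fraction the ratio falls below 1. With every death counted, the central case is (0.01 + 0.0495)/0.0795 = 74.8% v (0.01 + 0.0248)/0.0548 = 63.5%, a ratio of 0.85. The direction therefore depends on a rule that the documents do not give.

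**The case against.** The case against has five parts.

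1. **Two forms with two windows are not a contradiction.** A reader might infer that the forms conflict. Footnote f plans a 28-day snapshot and, for longer stays, a second form. The final form is also consistent with the open wording in section 2.1. This stands. What remains is that the tested endpoint has no fixed end and section 3.1 does not name its source.
2. **Arrests before transfusion.** A reader might infer from section 2.1 that these would be counted. Both visible forms tie the event to transfusion, so the documents do not support that for Group A. For Group B no form is shown.
3. **The mechanism and the forms belong to different groups.** The 25% v 50% contrast is Group B's, while the forms are Group A's, and section 3.1 expects few deaths in Group A. This stands: the survival argument is weak in Group A, and the discrepancy between forms is unverified in Group B. In Group B the argument rests on the open endpoint wording and inpatient-only collection.
4. **The numbers are assumed.** A reader might infer a settled bias against high IgG. The hazards have no source, step 6 shows that the sign can change, and the illustration holds discharge equal across IgG. If high IgG also speeds discharge, the gap shrinks. This stands.
5. **Materiality.** This is one of 16 secondary tests at 0.3%, and no primary endpoint is touched. This stands and limits the weight of the point.

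The objection does not answer the core. Followed as written, the rule gives each patient a different observation period, and the analysis does not adjust for it.

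**Conclusion.** The point holds as a definitional weakness in a secondary endpoint. The open window varies with survival and length of stay, and in Group B the plan itself expects survival to differ by IgG.

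The size and direction cannot be fixed from the documents. If arrest and discharge hazards are equal across IgG and terminal arrests are excluded, a null effect shows as a risk ratio of about 1.3 to 1.6 under the open window and 1.2 to 1.3 with a 28-day cap. If enough deaths are recorded as arrests, the ratio falls below 1. It would be wrong to conclude that a cap restores a ratio of 1: death and discharge still shorten the time at risk within 28 days.

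Both primary endpoints have a 28-day horizon in section 2.1 and are not affected. The priority is low, but the correction is nearly free.

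**What to change.** - **Section 2.1, both groups:** replace the open wording for arrest with a window from start of transfusion to day 28, and give renal and liver failure the same window.
- **Section 3.1:** name the 28-day outcome form as the source for all three endpoints, and confirm that the Group B form carries the same window.
- **Terminal arrest:** state whether an arrest at death counts.
- **Death:** treat it as a competing event, or report arrest-or-death as a sensitivity analysis.
- **Day-28 call (section 2.2):** ask about these events when early-discharged patients are phoned, so that observation does not stop at discharge.
- **After day 28:** report events from the final form descriptively.

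The cost is protocol and SAP wording plus a few questions in a call that is already planned; no visit is added. A few arrests after day 28 leave the tested count. The cap alone only reduces the distortion, which is why the handling of death belongs in the same change.
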